## 11.2.2.3. Severity of the Adverse Event

Severity (intensity) of the AE will be assessed according to the following scale:

- Mild: awareness of sign or symptom, but easily tolerated
- Moderate: discomfort sufficient to cause interference with normal activities
- Severe: incapacitating, with inability to perform normal activities

It is important to distinguish between serious and severe AEs. Severity is a measure of intensity whereas seriousness is defined by the criteria under Section 11.2.1.4. An AE of severe intensity may not be considered serious.

## 11.2.2.4. Expectedness

AEs will be evaluated as to whether they are anticipated or unanticipated. The assessment is performed by the sponsor and in this study it is based on the list of adverse device effects in the IFU of ALOCROSS® which acts as a Reference Safety Information (RSI). Only allergic or hypersensitivity reactions to its components may be observed according to the IFU.

- **Expected:** An AE is anticipated when the nature or severity of which is consistent with the applicable product information.
- **Unexpected:** An AE is unanticipated when the nature or severity of which is not consistent with the applicable product information.

## 11.2.3. Reporting of Safety Information

## 11.2.3.1. Recording and Reporting of Adverse Events

- 1. The sponsor or its designee shall fully record all of the following:
  - a) any adverse event of a type identified in the clinical investigation plan as being critical to the evaluation of the results of that clinical investigation;
  - b) any serious adverse event;
  - c) any device deficiency that might have led to a serious adverse event if appropriate action had not been taken, intervention had not occurred, or circumstances had been less fortunate;
  - d) any new findings in relation to any event referred to in points (a) to (c).
- 2. The sponsor or its designee shall report, without delay to all Member States in which the clinical investigation is being conducted, all of the following:
  - a) Until 25th of May 2021: any serious adverse event with the investigational device, the comparator or the investigation procedure **regardless of relatedness**;
  - b) From 26th of May 2021: any serious adverse event that has **a causal relationship** with the investigational device, the comparator or the investigation procedure or where such causal relationship is reasonably possible;
  - c) As from 26th of May 2021 follow-up reports for events that have earlier been deemed "not related" are no longer submitted.

- d) any device deficiency that might have led to a serious adverse event if appropriate action had not been taken, intervention had not occurred, or circumstances had been less fortunate;
- e) any new findings in relation to any event referred to in points (a) to (d).

The period for reporting shall take account of the severity of the event. Where necessary to ensure timely reporting, the sponsor or its designee may submit an initial report that is incomplete followed up by a complete report.

Upon request by any Member State in which the clinical investigation is being conducted, the sponsor or its designee shall provide all information referred to in paragraph 1.

3. The sponsor or its designee shall report any event as referred to in paragraph 2. Upon receipt, this report shall be sent electronically to all Member States in which the clinical investigation is being conducted.

The CRO ITEC Services will record all SAEs and Pregnancy reports and will inform Sponsor about received reports as soon as possible, not later than 1 work day from the first awareness of the event. At the same time, Santen will record any SAEs to Santen safety database. Santen will then perform medical review. ITEC Services will take care of the reporting to EC and CA.

The sponsor is responsible for ongoing safety evaluation of the study device. If there is at least a reasonable possibility that the event is related to the study device and it is both serious and unanticipated (USADE), ITEC services shall initiate expedited reporting, as soon as the medical review is finalized by Santen, according to applicable reporting requirements to all relevant parties, including regulatory authorities and ethics committees. Reporting responsibilities are described in the study specific safety management plan.

Investigators will also be notified of all suspected, unanticipated serious study device –related adverse device effects (USADEs) that occur during the clinical trial.

All serious and non-serious AEs, must be reported on the adverse event electronic case report form (AE e-CRF). In addition, any SAEs, any Device Deficiency that might have led to an SAE if suitable action had not been taken/intervention had not been made/if circumstances had been less fortunate, any new findings/updates in relation to already reported events - must be reported expeditedly to the sponsor (Section 11.2.3.3).

For each AE, the investigator will evaluate and report

- The date site became aware of the event
- The AE/safety information term (verbatim)
- The onset date
- Outcome of event
- The end date, if applicable
- Severity
- Location (e.g. right/left eye, both eyes, or not applicable if non ocular event)

- Causality to study devices (Not related/Unlikely/Possible/Probable/Causal Relationship)
- Causality to artificial tears (Not related/Unlikely/Possible/Probable/Causal Relationship)
- Relationship to study procedures (Not related/Unlikely/Possible/Probable/Causal Relationship)
- Action taken with the study device (for AEs only)
- Seriousness
- Treatment medications, if applicable
- Historical/concurrent medical conditions relevant for the AE
- Whether or not AE caused the patient to discontinue the study.

The AE term should be reported in standard medical terminology when possible.

If known, the diagnosis (i.e., disease or syndrome) must be recorded rather than component signs and symptoms (e.g., record as "worsening of cataract" rather than "drop in vision"). However, other events that are considered unrelated to an encountered syndrome or disease should be recorded as individual AEs (e.g., if worsening of macular edema and worsening of panuveitis are observed at the same time and are clinically unrelated, each event should be recorded as an individual AE).

# 11.2.3.2. Reporting of Pregnancy

Spontaneously reported pregnancy in a patient must be recorded in the source documents at the investigation site and reported expeditedly to ITEC services (Section 11.2.3.3).

Pregnancy in itself is not regarded as an AE unless there is a suspicion that an investigational device may have interfered with the effectiveness of a contraceptive medication. The pregnancy which occurs during the study or within 14 days of completing the study must be reported.

The outcome of all pregnancies (spontaneous miscarriage, elective termination, normal birth or congenital abnormality) must be followed up and documented even if the patient was discontinued from the study presuming that the informed consent is obtained for this from the patient. The outcome (health of infant) must also be reported to ITEC services.

All reports of congenital abnormalities/birth defects are SAEs. Spontaneous miscarriages should also be reported and handled as SAEs. Elective abortions without complications should not be handled as AEs.

## 11.2.3.3. Expedited reporting

The investigator must complete, sign and date the SAE (or Pregnancy) pages, verify the accuracy of the information recorded on the SAE (or Pregnancy) pages, and send a copy by e-mail or fax to ITEC services:

#### **ITEC SERVICES**

Email to [contact] or

Fax to [name] ([contact])

The CRO ITEC Services will record all SAEs and Pregnancy reports and will inform Sponsor about received reports as soon as possible, not later than 1 work day from the first awareness of the event. At the same time, Santen will record any SAEs to Santen safety database. Santen will then perform medical review. ITEC Services will take care of the reporting to EC and CA.

Additional follow-up information, if required or available, should all be sent by e-mail or faxed to ITEC Services immediately but no later than within 24 hours of receipt and this should be completed on a follow-up SAE (or Pregnancy) form and placed with the original information and kept with the appropriate section of the eCRF and/or study file.

The sponsor is responsible for ongoing safety evaluation of the study device. If there is at least a reasonable possibility that the event is related to the study device and it is both serious and unanticipated (USADE), ITEC services shall initiate expedited reporting, as soon as the medical review is finalized by Santen, according to applicable reporting requirements to all relevant parties, including regulatory authorities and ethics committees. Reporting responsibilities are described in the study specific safety management plan.

Investigators will also be notified of all suspected, unanticipated serious study device –related adverse device effects (USADEs) that occur during the clinical trial.

# 11.3. Documentation of Safety Information

All AEs will be recorded during the study in the patient's medical records and on the appropriate AE eCRF at the investigational site. Pregnancies will be recorded in the source documents. The sponsor records all SAEs and Pregnancy reports in the safety database of Santen.

ITEC records all AEs (including SAEs, ADEs etc.) during the study. Santen records all SAEs during the study.

At the end of the study ITEC will send all AEs (including SAEs, ADEs etc.) to Santen.

## 12. STATISTICS

#### 12.1. General Considerations

Unless specified otherwise, efficacy measures will be summarized by planned treatment, and safety measures will be summarized by actual treatment received. Continuous variables will be summarized using descriptive statistics such as number of observations (n), mean, standard deviation, median, minimum, and maximum. Categorical variables will be tabulated using frequency (n) and percent (%). For the variables recorded for both eyes, the descriptions will be given separately for the study eye and for the fellow eye, when considered relevant.

All data manipulations and descriptive summaries will be performed using SAS Version 9.4 or later.

A Statistical Analysis Plan (SAP) will be written and finalized before the start of the analysis of the study data, which will present the details of how all the analyses will be performed.

## 12.1.1. Sample Size

The sample size calculation was performed in order to test the non-inferiority of ALOCROSS® versus VISMED®, a commonly used preservative free artificial tear treatment in France for patients with keratitis or keratoconjunctivitis, on the main criterion (ocular surface staining score, the sum of the temporal and nasal interpalpebral conjunctival and corneal fluorescein staining graded using the modified Oxford scale). A standard deviation of 2.5 is expected for this parameter.

With an alpha risk of 0.025 (unilateral test of comparison versus the non-inferiority margin), a power of 90% and a non-inferiority (NI) margin of 2 points, a sample-size of 66 patients was found necessary.

To reach this sample-size in the per protocol population (population of interest in a NI study), a sample-size of 80 patients will be randomised in this study, to allow 15% of patients to be excluded from this population (withdrawals, major deviations...).

# **12.1.2. Study Eye**

The study eye is defined as the eligible eye that fulfils all the criteria listed under the inclusion criteria #4 and #5. If both eyes are eligible, the eye with the highest baseline CFS score will be chosen. If both eyes have the same baseline CFS score, the eye with the lowest Schirmer's test value will be chosen. If both eyes have the same Schirmer's test value, the right eye will be chosen as the study eye.

All the efficacy analyses will be performed on the study eye only.

# 12.2. Analysis Populations

Analysis populations are defined below:

- The **Full Analysis Set (FAS)** population consists of all randomised patients who received at least one dose of the study device and had at least one post-baseline sign or symptom assessment of the study eye. This will be the population used for efficacy analyses.
- The **Per-Protocol Set (PPS)** will be a subset of FAS, restricted to the patients who fulfil the protocol in the terms of the eligibility, interventions, and outcome assessment. It will be the analysis population for some sensitivity analyses. The determination of the PPS will be done before unmasking.
- The **Safety population** consists of all patients enrolled who received at least one dose of the study device. It will be the analysis population for safety analyses.

# 12.3. Analysis of Demographics and Baseline Characteristics

Descriptive summaries will be performed for demographic (including age, gender, female patients' menopausal status) and baseline characteristics variables (including time since diagnosis, past surgery or laser treatment in the study eye, and smoking status) by each FAS and safety population.

ALOCROSS® Protocol Version 2
ALHENA study 06 July 2020

In addition, medical history (ocular and systemic) and prior and concomitant medication uses will be summarised. Prior medication is defined as any medication or medical device that was used by the patients that is discontinued before the Baseline visit (Day 1).

# 12.4. Analysis of Primary Endpoint

The main hypothesis to be tested is the non-inferiority of ALOCROSS® versus VISMED® on the change from baseline (CFB) for the ocular surface staining score, after 4 weeks of treatment:

 $H0: (ALOCROSS^{\mathbb{R}} CFB - VISMED^{\mathbb{R}} CFB) > 2$ 

Ha: (ALOCROSS® CFB – VISMED® CFB) <= 2

An MMRM model will be performed to provide the estimate of the least square (LS) means difference between groups in the change from baseline of the ocular surface staining score after 4 weeks of treatment. This model will include the treatment, visit, and treatment-by-visit interaction as fixed factors, the ocular surface staining score at the baseline and the interaction between the treatment and the ocular surface staining score at baseline as covariates.

The 95% confidence interval (CI) of this difference will then be computed and the upper bound will be compared to the NI margin (2 points). In case where the upper bound will be found less than or equal to the NI margin, the NI of ALOCROSS® versus VISMED® will be demonstrated.

Positive results on the FAS population will be confirmed in the PP population, as for a NI study the two sets of analysis have the same importance (ref. ICHE9).

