## 4. INTRODUCTION

Since the 2017 International Dry Eye Workshop (DEWS), the term dry eye disease (DED), also known as keratoconjunctivitis sicca, describes "a multifactorial disease of the ocular surface characterised by a loss of homeostasis of the tear film. This loss is accompanied by ocular symptoms, in which tear film instability and hyperosmolarity, ocular surface inflammation and damage, and neurosensory abnormalities play etiological roles (DEWS 2017a (1))". The prevalence of DED ranges from 5% to 50% (DEWS 2017b (2)), and it has become one of the principal causes for ophthalmic consultation.

First-line treatments of dry eye focus on the relief of symptoms of ocular discomfort. One of the most extended treatment is instilling artificial tears onto the eye (Dry Eye Syndrome Guidance, 2016 (3)). A variety of solutions with different compositions are available on the market. Hyaluronic acid is an agent used in some eyedrops because of its water retention and lubricant properties, which allow increasing corneal wettability in dry eye patients (Nakamura, 1993 (4)). Several studies have proved the efficacy of hyaluronic acid in achieving improvement in both ocular discomfort symptoms and ocular signs, with good tolerance (Baeyens, 2012 (5); Vogel, 2010 (6); Brignole, 2005 (7); Sand, 1989 (8)). However, the benefit of using eyedrops containing hyaluronic acid over other artificial tears, including saline has not been largely evidenced (Doughty, 2014 (9)). A recent phase III, randomised, crossover, double-blind study by Pinto-Fraga et al showed that Visaid 0.2% was effective in improving some clinical symptoms and signs in comparison with the use of 0.9% saline solution in mild dry eye patients during a 1-month management period (Pinto-Fraga, 2017 (10)). The most important difference was the significant decrease in corneal and conjunctival staining induced by Visaid 0.2%. Additionally, the safety of the solution was proved.

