# 7. SELECTION AND WITHDRAWAL OF PATIENTS

#### 7.1. Patient Inclusion Criteria

Patient eligibility is determined according to the following criteria:

- 1. Male or female patient aged 18 years or above.
- 2. Patient using artificial tears for at least 3 months prior to the Screening visit.
- 3. Patient experiencing at least 2 symptoms of ocular discomfort rated ≥23 mm on the 0 to 100 mm visual analogue scale (VAS) (among itching, eye dryness, sticky feeling, photophobia, pain, burning or stinging, sandy feeling or grittiness, or foreign body sensation) at Screening and Baseline visits.
- 4. OSS score (sum of nasal and temporal interpalpebral conjunctival and corneal vital staining) ≥4 and ≤9 on a modified Oxford scale at Screening and Baseline visits in at least one eye.
- 5. TBUT of  $\leq$ 10 seconds at Screening and Baseline visits and/or Schirmer's tear test of  $\geq$ 3 and  $\leq$ 9 mm/5 min at Screening visit in the same eye that fulfil inclusion criteria #4.
- 6. The patient has signed and dated a written informed consent form prior to the initiation of any study procedures.

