# 8.1.3. Description of artificial tears, LARMABAK®

LARMABAK® is a sterile unpreserved solution for topical ophthalmic use, containing NaCl at 0.9% (0.9 g/100 mL). LARMABAK® will be purchased from a commercial source.

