# 9.1. Screening visit (V1): 14 to 7 days before the Baseline visit

- Written informed consent
- Demographic information
- Ocular and systemic medical history
- Previous and concomitant ocular and systemic medications [including artificial tears (AT) usage]
- Verify inclusion and exclusion criteria based on the evaluations just performed:
  - Patients fulfilling the inclusion criteria will discontinue all previous treatments related to dry eye including artificial tears and any prohibited ocular treatments and receive study specific artificial tears for 7 to 14 days
  - o Patients **not fulfilling** the inclusion criteria will be considered as having failed the screening and will not be included in the study
- Filling by the patient of the VAS for the symptoms evaluation of ocular discomfort
- BCDVA
- Slit lamp examination

ALOCROSS® Protocol Version 2
ALHENA study 06 July 2020

- TBUT
- Ocular surface staining score (corneal fluorescein staining and nasal and temporal interpalpebral conjunctival staining (modified Oxford scale))
- Schirmer's test (without anaesthesia)
- IOP
- Dispensation of unpreserved artificial tears (LARMABAK®)
- Patients will be scheduled to return to the site in 7 to 14 days for the Baseline visit.

# 9.2. Baseline visit (V2): Day 1

- Collection of the artificial tears bottle
- Inclusion/exclusion criteria review
- Record of previous and concomitant ocular and systemic medications [other than artificial tear (AT) usage]
- Record adverse events (AEs)
- Filling by the patient of the VAS for the symptoms evaluation of ocular discomfort
- Completion by the patient of the Quality of life questionnaire NEI-VFQ
- BCDVA
- Slit lamp examination
- TBUT
- Ocular surface staining score (corneal fluorescein staining and nasal and temporal interpalpebral conjunctival staining (modified Oxford scale))
- IOP
- Urine pregnancy test (women of childbearing potential only)
- Randomisation in IWRS
- Dispensation of masked study device for a 4-week period according to the randomisation number
- Patients will be scheduled to return to the site in 2 weeks (Day 14 +/-3 days) for the first follow-up visit (V3)

# 9.3. Follow-up visit: Visit 3: Day 14

- Record of concomitant ocular and systemic medications
- Record adverse events (AEs)
- Ocular surface staining score (corneal fluorescein staining and nasal and temporal interpalpebral conjunctival l staining (modified Oxford scale))
- Assessment of compliance to study device

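### Does the 2-point non-inferiority margin, given without a rationale or a condition on VISMED's own change, need a change to the plan?

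*Protocol*

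**What the plan says.** Section 12.4 tests the difference in mean change from baseline in OSS, ALOCROSS minus VISMED, with the alternative "Ha: (ALOCROSS® CFB – VISMED® CFB) <= 2". A negative change is an improvement. For the decision, the 95% confidence interval is taken from the MMRM and "the upper bound will be compared to the NI margin (2 points"; a positive result in the full analysis set (FAS) is to be confirmed in the per-protocol set (PPS).

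Section 12.1.1 uses "a non-inferiority (NI) margin of 2 points, a sample-size of 66 patients was found necessary", and adds "A standard deviation of 2.5 is expected for this parameter". It randomises 80 so that 15% can be lost from the PPS. Neither the synopsis, section 12.1.1 nor section 12.4 says why 2 points was chosen, or what effect VISMED is expected to have on OSS.

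Before baseline, patients stop their own tears and "receive study specific artificial tears for 7 to 14 days". Section 8.1.3 describes that product as a "sterile unpreserved solution for topical ophthalmic use, containing NaCl at 0.9" per cent solution, that is, saline. Entry requires an OSS score "≥4 and ≤9 on a modified Oxford scale at Screening and Baseline visits in at least one eye". After randomisation there are two arms, ALOCROSS and VISMED.

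On evidence, the Introduction states: "Several studies have proved the efficacy of hyaluronic acid in achieving improvement in both ocular discomfort symptoms and ocular signs". It then says that the advantage of hyaluronic acid over other tears, saline included, is not well documented. It goes on to describe a randomised double-blind crossover study in mild dry eye, in which a 0.2% hyaluronic acid product reduced corneal and conjunctival staining relative to saline. No effect size in OSS points is given.

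**The concern.** A non-inferiority margin should be smaller than the effect the active control can be relied on to have; otherwise a useless product can pass. Here the margin is 2/2.5 = 0.8 of the planned SD. Against the entry range of 4 to 9, it is 2/9 = 22% to 2/4 = 50% of complete clearing. If patients left on saline would have worsened by 1 point, the shares fall to 2/10 = 20% and 2/5 = 40%.

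The hypotheses sharpen the worry. Let ALOCROSS have a true mean change of 0 from its saline-treated baseline and VISMED a true change of -2. The difference is 0 - (-2) = 2, which lies in the alternative. A product with no effect beyond the run-in saline is therefore non-inferior by definition for any true VISMED improvement up to 2 points. The protocol has no saline arm to expose this, gives no expected VISMED effect, and sets no condition on the VISMED change. At stake is whether a positive result shows that ALOCROSS works, or only that neither arm moved much.

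The natural remedies would be to state the basis of the margin, to report VISMED's own change beside the difference, and to withhold a claim of preserved efficacy unless VISMED improves by more than 2 points.

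**Working it through.** **1. The plan's own figure.** Inputs from section 12.1.1: one-sided alpha 0.025, power 90%, margin 2, SD 2.5. A true difference of 0 is assumed, since none is stated.

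n per arm = 2 × ((1.960 + 1.282) × 2.5 / 2)² = 32.8, rounded up to 33; total 66. This reproduces the protocol. With 80 randomised and 15% lost, 80 × 0.85 = 68 remain, or 34 per arm.

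**2. Hypothesis against decision rule.** The half-width of the 95% interval for the difference is t × 2.5 × √(2/n):

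| n per arm | SE | half-width | largest observed deficit that passes |
|---|---|---|---|
| 34 (PPS) | 0.606 | 1.211 | 2 - 1.211 = 0.79 |
| 40 (FAS) | 0.559 | 1.113 | 2 - 1.113 = 0.89 |

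An unchanged ALOCROSS arm thus passes only if VISMED's observed improvement is about 0.8 to 0.9 points or less. At an observed improvement of 2, the upper bound is about 3.1 to 3.2 and the trial fails. If baseline adjustment reduced the SD to 2.0 (assumed), the PPS limit would be 2 - 0.968 = 1.03.

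**3. Chance that an unchanged arm passes.** ALOCROSS true change 0, SD 2.5, normal data, FAS 40 per arm, PPS a random 34 per arm, both required. VISMED's true improvement is not in the protocol, so a range is shown (simulation):

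| True VISMED improvement | FAS | PPS | both |
|---|---|---|---|
| 0.5 | 75% | 68% | 66% |
| 1.0 | 42% | 37% | 33% |
| 1.5 | 14% | 12% | 10% |
| 2.0 | 2.5% | 2.5% | 1.6% |

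The risk is real only if VISMED itself does little, roughly 1 point or less. The protocol does not say that this is so.

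**4. What a reader needs for interpretation.** The quantity to hold against VISMED's effect is the observed upper bound, not the margin. If the upper bound is 0.5, the data are compatible with a loss of at most 0.5 points, and a VISMED effect above 0.5 is enough for ALOCROSS to retain some of it. A VISMED effect above 2 is not required.

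**5. What a 2-point condition on VISMED would do.**

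- *Not necessary.* If saline patients would worsen by 1 point, a VISMED change of -1.5 is an effect of 2.5 points, yet the condition fails.
- *Not sufficient.* Patients are selected on OSS of at least 4 at two visits, so part of any fall can be regression to the mean.
- *Costly.* The VISMED mean has a 95% half-width of 0.87 (34 per arm) or 0.80 (40 per arm) and would be held to a hard cut. With equal arms, SD 2.5, 200,000 simulated trials:

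| n per arm | NI alone | NI and VISMED > 2, true improvement 2.0 | 2.2 | 2.5 |
|---|---|---|---|---|
| 34 | 90% | 41% | 58% | 78% |
| 40 | 94% | 44% | 63% | 84% |

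**6. What is already planned.** The synopsis, under the criteria for evaluation, provides for following the course within each group. Section 12.6 summarises OSS and its change from baseline by arm and visit. VISMED's own change will therefore be in the report.

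**The case for a change.** The strongest case for a change is that the margin is the central assumption of a non-inferiority trial. The protocol fixes it, sizes the trial on it and tests against it, so its basis is not a detail that can be left to the SAP. The Introduction itself doubts how well hyaluronic acid has been shown to beat saline. If both arms barely move, section 12.4 will still call non-inferiority demonstrated, and any caution voiced then will look like an afterthought. Stating the basis, and printing VISMED's LS mean change with its interval, would cost a few sentences and no patients.

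Much of this stands. The margin is a bare number, the PPS faces the same margin and adds no protection on this point, and section 12.6 is descriptive without a criterion. A sentence of justification would make the protocol easier to defend.

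It does not carry as far as a required change. The justification would explain the margin and alter neither the test nor its outcome. The protocol contains no figure showing that 2 points is too wide, and the saline-controlled study cited in the Introduction, though of another product in milder disease, points to an effect on staining. The VISMED change is already to be reported; the LS mean with its interval is an ordinary output of the planned model. Only the condition on VISMED's change would alter conclusions, and it is a disputable trade-off with a large loss of power.

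**Conclusion.** No change to the plan follows. The margin lacks a stated rationale, and the alternative hypothesis does contain an unchanged ALOCROSS arm for any true VISMED improvement up to 2 points. But the confidence-bound rule confines a pass to an observed VISMED advantage of about 0.8 to 0.9 points, and the chance of passing falls to 2.5% per analysis set, 1.6% for both, if VISMED truly improves by 2 points. Whether 2 points exceeds VISMED's whole effect cannot be settled from the protocol, in either direction.

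The remedies divide into missing explanation, reporting that is largely planned already, and a 2-point condition that is neither necessary nor sufficient and would take the chance of a positive reading from 90% to between 41% and 78% for true improvements of 2.0 to 2.5 points (34 per arm). A reader of the results can judge the matter by setting the observed upper bound beside VISMED's own change, allowing for regression to the mean and for what saline alone might have done.

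These figures assume normal data, an SD of 2.5, no gain from baseline adjustment and 34 to 40 patients per arm. A smaller adjusted SD moves the passing limit closer to 2 but keeps it below.
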